Timepoints by study Month	Day 1	Month 12	Day 695	Month 24	Month 25	Month 26	Month 37	Month 49	Event driven
Record SAEs and pIMDs post- revaccination (section 12.5.9)				•	•	•	•		
Record pregnancies and pregnancy outcomes (sections 8.1.13 and 12.5.9.1)	•	•		•	•	•	•	•	
Record SAEs related to study participation, or to a concurrent GSK medication/vaccine	•	•		•	•	•	•	•	
Record SAEs related to study vaccine (section 12.5.9)	•	•		•	•	•	•	•	
Record intercurrent medical conditions, including HZ cases (section 7.6)	•	•		•	•	•	•	•	
Record AESI: biopsy-proven allograft rejection (section 8.1.14)	•	•		•	•	•	•	•	
HZ assessments only in case of a clinically diagnosed suspected HZ									
Return HZ-specific diary cards and ZBPI questionnaires to study staff/investigator									0
Transcription of the HZ-specific diary card and ZBPI questionnaires by study staff/investigator ^e		•		•	•	•	•	•	•
Take digital photographs of HZ rash and upload to e-Clinipix (section 8.1.15)									•
Collect HZ lesion samples (from 3 separate lesions) for confirmation by PCR (section 8.1.15)									•
Record relevant information regarding HZ ^e		•		•	•	•	•	•	•
Record any medical attention received for HZ or any HZ-related complication									•

CONFIDENTIAL

212340 (ZOSTER-073 EXT:041 Y4-10)
Protocol Amendment 1 Final

Epoch	Epoch 001			Epoch 002					
Study Phase	Long-Term Follow-up Phase			Revaccination Phase			Follow-up Phase		
Type of contact	Visit 1	Visit 2	PC1 ^a	Visit 3 ^b	Visit 4 ^{c, h}	Visit 5 ^{c, h}	Visit 6 ^c	Visit 7 ^c	Ad-hoc HZ Visit ^d
Timepoints by study Year	Day 1	Year 1	35 days prior Year 2	Year 2	Year 2 + 1 month	Year 2 + 2 months	Year 3 + 2 months	Year 4 + 2 months	
Timepoints by study Month	Day 1	Month 12	Day 695	Month 24	Month 25	Month 26	Month 37	Month 49	Event driven
Phone contact follow-up of HZ rash and HZ pain resolution (section 8.1.15) ^e		O		O	O	O	O	O	
Record the resolution date of HZ rash ^e		•		•	•	•	•	•	•
Primary Study Conclusion						•			
Final Study Conclusion								•	

Note: The double-line borders indicate analyses that will be performed on all data obtained up to this time point (refer to section 10.4).

• is used to indicate a study procedure that requires documentation in the individual electronic Case Report Form (eCRF).

O is used to indicate a study procedure that does not require documentation in the individual eCRF.

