Secondary	
 Percentage of subjects with at least one local AE (solicited and unsolicited), with at least one general AE (solicited and unsolicited), and with any AEs during the solicited 7-day follow-up period will be tabulated with exact 95% CI after each revaccination dose and overall. The same computations will be done for Grade 3 AEs. Percentage of subjects reporting each individual solicited local AE (any grade and Grade 3) and solicited general AE (any grade, Grade 3, any related and Grade 3 related) during the 7-day follow-up period (i.e., on the day of revaccination and 6 subsequent days) will be tabulated after each revaccination dose and overall. Duration of solicited local and general AEs within 7 days and entire duration will be tabulated overall. Percentage of subjects with any unsolicited AEs during the 30-day follow-up period (i.e., on the day of revaccination and 29 subsequent days) with its exact 95% CI will be tabulated by Medical Dictionary for Regulatory Activities (MedDRA) preferred term. Similar tabulation will be done for Grade 3 unsolicited AEs, for any causally related unsolicited AEs, for Grade 3 causally related unsolicited AEs, for Grade 3 non-serious unsolicited AEs, for Grade 3 causally related non-serious unsolicited AEs and for unsolicited AEs resulting in a medically attended visit. Percentage of subjects with at least one report of SAE classified by the MedDRA SOC and PTs and reported from revaccination Dose 1 up to 30 days and 12 months post- last revaccination dose will be tabulated with exact 95% CI. SAEs will be also described in detail. Percentage of subjects with at least one report of causally related-SAE classified by the MedDRA SOC and Preferred Terms and reported from revaccination Dose 1 up to 30 days and 12 months post-last revaccination dose, and up to study end (Month 49) will be tabulated with exact 95% CI. Related-SAE will be also described in detail. Percentage of subjects with at least one pIMD classified by the MedDRA SOC and Preferred Terms and percentage of subjects with at least one pIMD with causal relationship, reported from Dose 1 up to 30 days and 12 months post- last revaccination dose will be tabulated with exact 95% CI. Percentage of subjects with at least one biopsy-proven allograft rejection and causal relationship reported from Dose 1 up to study end (Month 49) will be tabulated with exact 95% CI. Percentage of subjects reporting unsolicited AEs resulting in a medically attended visit from Dose 1 up to 30 days post-last revaccination dose will also be tabulated with exact 95% CI. Fatal SAEs will be described by onset date of SAE and date of death SAEs (including fatal SAEs), pIMDs and withdrawal due to AE(s) will be described in detail. Listing of withdrawals due to AE and SAEs will be provided Listing of subjects with confirmed HZ episode will be provided. Listing of subjects with biopsy-proven allograft rejection will be provided.

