Subject Diary training should be directed at the individual(s) who will perform the measurements of AEs and who will enter the information into the Subject Diary. This individual may not be the subject/subjects' LAR(s), but if a person other than the subject/subjects' LAR(s) enters information into the Subject Diary, this person's identity must be documented in the subject's source record. Any individual that makes entries into the Subject Diary must receive training on completion of the Subject Diary at the time of the visit when Subject Diary is dispensed. This training must be documented in the subject's source record.

At each revaccination visit, a Subject Diary card will be provided to the subject or subjects' LAR(s). The subject or subjects' LAR(s) (or subject's caregiver) will be instructed to measure and record the oral body temperature, and any solicited local/general AEs (i.e. on the day of revaccination and during the next 6 days) or any unsolicited AEs (i.e. on the day of revaccination and during the next 29 days occurring after revaccination). The subject or subjects' LAR(s) (or subject's caregiver) will be instructed to return the completed Subject Diary card to the investigator at the next study visit.

- Collect and verify completed Subject Diary cards during discussion with the subject on Visit 4 (Month 25) and on Visit 5 (Month 26).
- Any unreturned Subject Diary cards will be sought from the subject through telephone call(s) or any other convenient procedure.
- The investigator will transcribe the collected information into the eCRF in English.

12.5.9.1. Time period for detecting and recording adverse events, serious adverse events and pregnancies

All AEs during 30 days following administration of each dose of study vaccine (from day of revaccination and 29 subsequent days) must be recorded into the appropriate section of the eCRF, irrespective of intensity or whether or not they are considered vaccination-related.

The time period for collecting and recording SAEs will begin at the first receipt of study vaccine at Visit 3 (Month 24) during revaccination phase and will end at Visit 6 (Month 37) for each subject (See section [12.5.10](#) for instructions on reporting of SAEs). However, any SAEs assessed as related to study participation (e.g. study treatment, protocol-mandated procedures, invasive tests, or change in existing therapy) or related to

CONFIDENTIAL212340 (ZOSTER-073 EXT:041 Y4-10)
Protocol Amendment 1 Final

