4.3.2.2. Revaccination phase

The results for the analysis of safety in the revaccination phase will be tabulated as follows:

- Number and percentage of subjects with at least one local AE (solicited and unsolicited), with at least one general AE (solicited and unsolicited), and with any AEs during the solicited 7-day follow-up period will be tabulated with exact 95% CI after each revaccination dose and overall. The same computations will be done for Grade 3 AEs and medically attended AEs. Number and percentage of subjects reporting each individual solicited local AE (any grade and Grade 3) and solicited general AE (any grade, Grade 3, any related and Grade 3 related) during the 7-day follow-up period (i.e., on the day of

[figure not shown]
revaccination and 6 subsequent days) will be tabulated after each revaccination dose and overall.

- Duration of solicited local and solicited general AEs within 7 days and entire duration (lasting longer than 7 days) will be tabulated descriptively overall.
- Number and percentage of subjects with any unsolicited AEs during the 30-day follow-up period (i.e., on the day of revaccination and 29 subsequent days) with its exact 95% CI will be tabulated by MedDRA Primary SOC and PT. Similar tabulations will be done for Grade 3 unsolicited AEs, for any causally related unsolicited AEs, for Grade 3 causally related unsolicited AEs, for Grade 3 non-serious unsolicited AEs, for Grade 3 causally related non-serious unsolicited AEs, non-serious unsolicited AEs, non-serious causally related unsolicited AEs, and for unsolicited AEs resulting in a medically attended visit.
 - The number and percentage doses followed by unsolicited AEs during the 30-day follow-up period with its exact 95% CI will also be tabulated.
- Number and percentage of subjects with at least one report of SAE classified by MedDRA Primary SOC and PT and reported from revaccination Dose 1 up to 30 days post-last revaccination dose, from revaccination Dose 1 up to 12 months post- last revaccination dose, and from revaccination Dose 1 up to study end will be tabulated with exact 95% CI.
- Number and percentage of subjects with at least one report of causally related-SAE classified by MedDRA Primary SOC and PT and reported from revaccination Dose 1 up to 30 days post-last revaccination dose, from revaccination Dose 1 up to 12 months post-last revaccination dose, and from revaccination Dose 1 up to study end will be tabulated with exact 95% CI.

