- Number and percentage of subjects with at least one pIMD classified by MedDRA Primary SOC and PT and percentage of subjects with at least one pIMD with causal relationship, reported from revaccination Dose 1 up to 30 days, from revaccination Dose 1 up to 12 months post-last revaccination dose, and from revaccination Dose 1 up to study end will be tabulated with exact 95% CI.
- Number and percentage of subjects with at least one biopsy-proven allograft rejection and biopsy-proven allograft rejection with causal relationship reported from revaccination Dose 1 up to study end will be tabulated with exact 95% CI.
- Number and percentage of subjects with at least one biopsy-proven allograft rejection and biopsy-proven allograft rejection with causal relationship reported from revaccination Dose 1 up to 12 months post last revaccination will be tabulated with exact 95% CI.
- Number and percentage of subjects with fatal SAEs and causally related fatal SAEs classified by MedDRA Primary SOC and PT will be presented. Fatal SAEs and related fatal SAEs will also be described by onset date of SAE and date of death as follows:
 - With onset date of fatal SAE during the period starting from revaccination Dose 1 to 30 days post last revaccination dose, from revaccination Dose 1 up to 12 months post last revaccination, and from revaccination Dose 1 up to study end

[figure not shown]
- Who died (date of death) during the period starting from revaccination Dose 1 up to 30 days post last revaccination dose, from revaccination Dose 1 up to 12 months post last revaccination, and from first revaccination to study end.
- SAEs and pIMDs will be listed. These listings will include all fields on the CRF, including but not limited to, verbatim event description, MedDRA SOC/PT, start/stop study days, site, intensity (maximum and at time of onset), relationship to study vaccine, outcome.
- Listing of withdrawals due to AE and SAEs will be provided, including verbatim event description, MedDRA SOC/PT, start/stop study days, site, intensity (maximum and at time of onset), relationship to study vaccine, outcome
- Listing of subjects with confirmed HZ episode from Dose 1 of revaccination (Month 24) up to study end will be provided.

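### The SAP reports all-cause SAE and pIMD percentages to Month 49, but the protocol stops routine collection of these events at Month 37

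*SAP*

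**What the plan says.** SAP 4.3.2.2 sets three windows for any SAE after revaccination: to 30 days after the last dose, then "up to 12 months post- last revaccination dose, and from revaccination Dose 1 up to study end will be tabulated with exact 95% CI". For pIMDs it repeats the pattern, "from revaccination Dose 1 up to 12 months post-last revaccination dose, and from revaccination Dose 1 up to study end will be tabulated", and the same sentence covers the causally related row: "percentage of subjects with at least one pIMD with causal relationship, reported from revaccination Dose 1 up to 30 days". Fatal SAEs, all-cause as well as related, are also taken to study end; by date of death the later windows run "up to 12 months post last revaccination, and from first revaccination to study end".

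The protocol stops earlier. Section 12.5.9.1 says SAE collection starts with the first revaccination dose "during revaccination phase and will end at Visit 6 (Month 37) for each subject". The same section ends pIMD collection at Visit 6, without distinguishing related from unrelated pIMDs. In the schedule of activities (Table 3), the row "Record SAEs and pIMDs post- revaccination (section 12.5.9") is marked at Visits 3 to 6 and not at Visit 7.

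The protocol's planned analysis in 10.3.4 matches that collection. SAEs are "reported from revaccination Dose 1 up to 30 days and 12 months post- last revaccination dose will be tabulated with exact 95% CI", and the pIMD row covers "at least one pIMD with causal relationship, reported from Dose 1 up to 30 days and 12 months post- last revaccination dose". Protocol Table 5 and SAP 1.1 both end the endpoints for SAEs (including fatal ones) and for pIMDs at Month 37. Only related SAEs, related fatal SAEs, biopsy-proven rejections and confirmed HZ run to Month 49.

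SAP 4.8, which records departures from the protocol analyses, does not mention the added study-end window.

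**The concern.** A percentage with an exact confidence interval is read as the incidence over the period in its title. Here the numerator is routinely collected for about the first half of that period and selectively afterwards, while every exposed subject stays in the denominator.

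Set beside the 12-month table, the study-end table could suggest that few new SAEs or pIMDs arise in the second year after revaccination, when part of them were simply not being asked for. The listings cannot repair this, because they show only what was recorded. The population is immunosuppressed transplant recipients given an adjuvanted vaccine, so readers are likely to look at longer-term safety.

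All-cause fatal SAEs have a milder form of the problem. The endpoint stops at Month 37, the table does not, and the SAP does not say by what route later deaths are collected.

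**Working it through.** **1. Windows.** Dose 2 is planned at Month 25. 25 + 12 = Month 37 and 25 + 24 = Month 49, which reproduces both visit months in the documents. From Dose 1 at Month 24:

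- labelled window: 49 − 24 = 25 months
- routine all-cause SAE and pIMD collection: 37 − 24 = 13 months
- remainder: 49 − 37 = 12 months; 12/25 = 48%

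These are nominal months. Protocol Table 8 allows Visit 7 to be moved or cancelled in special circumstances.

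**2. What still enters after Month 37.**

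| Route | Protocol source |
|---|---|
| Vaccine-related SAEs; SAEs related to study participation or a concurrent GSK product | 12.5.9.1 |
| AEs and SAEs leading to withdrawal | 12.5.9.1 |
| Biopsy-proven rejections | 12.5.9.1 |
| Intercurrent medical conditions, including HZ | 7.6, 12.5.9.1 |
| COVID-19 cases | 8.1.16 |
| Pregnancy outcomes that are SAEs | 12.5.12.3 |

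An unrelated SAE outside these routes has no route in. A related pIMD that is serious enters as a related SAE; a non-serious one has no dedicated route.

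**3. Illustration of size.** Neither document gives an SAE rate, a pIMD rate, the number revaccinated or the share of late events captured. All four are assumptions here. Let r be the 13-month risk and c the share of late first events captured. With a constant hazard:

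- true 25-month risk: T = 1 − (1 − r)^(25/13)
- value the table shows: r + c(T − r)

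| Assumed r | T | Table, c = 0.25 | Table, c = 0.75 |
|---|---|---|---|
| SAE 5% | 9.4% | 6.1% | 8.3% |
| SAE 10% | 18.3% | 12.1% | 16.3% |
| SAE 20% | 34.9% | 23.7% | 31.2% |
| SAE 30% | 49.6% | 34.9% | 44.7% |
| pIMD 1% | 1.9% | 1.2% | 1.7% |
| pIMD 2% | 3.8% | 2.5% | 3.4% |

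For SAEs the table shows 65% to 90% of the true value (6.1/9.4 at one end, 44.7/49.6 at the other).

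**4. In subjects, with Clopper-Pearson intervals, for the 20% SAE case.** SAP Table 1 gives 68 enrolled, an upper bound for the Exposed Set; 50 is an assumed smaller set.

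| | n = 68 | n = 50 |
|---|---|---|
| To Month 37 | 14 = 20.6% (11.7–32.1) | 10 = 20.0% (10.0–33.7) |
| Study end, c = 0.25 | 16 = 23.5% (14.1–35.4) | 12 = 24.0% (13.1–38.2) |
| Study end, full capture | 24 = 35.3% (24.1–47.8) | 17 = 34.0% (21.2–48.8) |

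With c = 0.75 and n = 68 the table shows 21 = 30.9% (20.2–43.3).

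**5. pIMDs in subjects.** The number missed out of 68 is 68(1 − c)(T − r). At r = 1% it is 0.47 (c = 0.25) or 0.16 (c = 0.75); at r = 2% it is 0.92 or 0.31.

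**The case against.** The strongest reply is that nothing planned as an endpoint is harmed. The SAE and pIMD endpoints stop at Month 37, the 30-day and 12-month tables are kept in full, and the whole analysis is descriptive. The study-end tables are extras. That is true, and it limits how serious the point is. It does not make the extra tables correctly labelled.

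Second, more late information may arrive than the routes listed above suggest. Interim medical history is taken through Visit 7, a directed examination is done at that visit with pertinent diagnoses entered in the eCRF, and intercurrent conditions are broadly defined. Open SAEs and AESIs are also reviewed to the last visit. However, interim history stays in source documents, and the review to last visit covers events already documented. Nothing says that examination findings feed the SAE or pIMD tables. These routes narrow the gap without closing it.

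Third, the size rests wholly on assumptions, and for pIMDs it is under one subject. Both points stand. The any-SAE row is the only one where the numbers could visibly move, and if every late event were captured there would be no bias.

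Fourth, later deaths would probably be recorded as events leading to withdrawal. I agree, and so ask only for a note on that row.

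Finally, cutting the tables at Month 37 would drop reported late events from the summaries. That is a fair reason to prefer the footnote.

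**Conclusion.** The mismatch is established from the text alone: 25 months are labelled, 13 are routinely collected, and 12 (48%) are covered selectively. It applies to any SAE, any pIMD and causally related pIMD. The study-end windows for related SAEs, related fatal SAEs and biopsy-proven rejections agree with the protocol's collection and are not in question.

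The direction of the error is towards understatement. Its size cannot be fixed from the documents. Under a constant hazard, assumed 13-month SAE risks of 5% to 30% and 25% to 75% late capture, the SAE row would show 65% to 90% of the true 25-month risk. For pIMDs the effect is mainly one of labelling. The Month 37 results stand as planned. This should be corrected before the tables are produced, but it does not threaten the trial's endpoints.

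**What to change.** In SAP 4.3.2.2, choose one of two edits for any SAE, any pIMD and causally related pIMD:

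- end the percentages and intervals at 12 months after the last dose (Month 37), and list later reported events without a percentage or interval; or
- keep the study-end tables with a footnote stating which events were still collected after Month 37 and that the figures are not an incidence over the full period.

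Keep the study-end windows for related SAEs, related fatal SAEs and biopsy-proven rejections. For all-cause fatal SAEs to study end, add a footnote that the endpoint stops at Month 37 and that later deaths are expected through the collection of events leading to withdrawal. If any added window is retained, an entry in SAP 4.8 would be good practice but is secondary.

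The cost is SAP wording only: three rows end one window earlier or carry one footnote, plus one footnote on the fatal SAE row. No data collection changes.

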4.5. Other Safety Analyses

Safety analyses will be performed on the Enrolled Set for the LTFU phase. For the revaccinated subjects the Exposed Set for revaccination phase will be used. For non-revaccinated subjects, the Enrolled Set will be used to compare to revaccinated subjects past ZOSTER-073 Visit 3.

4.5.1. Extent of Exposure

The number of subjects receiving each revaccination dose will be tabulated as part as subject disposition and compliance. See Section [6.1.1](#) and Section [6.1.5](#) for more details.

4.5.2. Adverse Events

Adverse event analyses are described in Section [4.3.2](#).

Adverse events will be coded using the standard Medical Dictionary for Regulatory Activities (MedDRA) and graded by the investigator. Intensity scales for solicited local and solicited general events can be found in protocol section 12.5.9.1.2.

4.5.2.1. Adverse Events of Special Interest

For this trial, AESIs will be defined as:

- potential immune-mediated diseases
- renal allograft rejection (biopsy proven)

Analyses of these events are described in Section [4.3.2](#).

4.5.2.2. COVID-19 Assessment

The number of subjects with suspected, probable, or confirmed COVID-19 infection will be presented along with number of subjects with positive, negative, or indeterminate diagnosis test results.

A standardized MedDRA Query (SMQ) will be used to identify all AEs related to COVID-19. The overall incidence of AEs and SAEs of COVID-19 and COVID-19 AEs leading to study intervention discontinuation or study withdrawal will be summarized.

4.5.2.3. Impact of COVID-19 Pandemic on Safety Results

Pandemic measures began in different countries at different times. A dataset containing the date when pandemic measures began, as determined by the GSK country Issue Management Teams (IMT), will be used to determine the start date of each wave of pandemic measures within each country.

4.5.3. Additional Safety Assessments

4.5.3.1. Laboratory Data

Allograft dysfunction will be assessed through serum creatinine measurements. The number and percentage with an increase from baseline (≥ 1.2 , ≥ 1.5 , ≥ 1.75 , ≥ 2 fold) in serum creatinine related to allograft rejection episodes, revaccination, and HZ episodes. will be tabulated based on whether the episode fell in the time frames outlined in Section [4.3.2.1](#) and Section [4.3.2.2](#)

See Section 6.2.3 for definitions of baseline and handling post-baseline measurements related to rejection episodes, revaccination, and HZ episodes.

A listing of raw serum creatinine measurements and their corresponding fold increase from baseline will be provided for each individual subject. Changes from baseline and percent changes from baseline will also be included for each subject, along with their primary and revaccination dates, if applicable.

Replacement kidney since ZOSTER-041 will also be listed.

